10.0 Data and Specimen Banking

10.1 Storage of specimens.

Blood specimens for long-term storage will be stored in a freezer belonging to [name] research program at Northwestern University, in the freezer farm in the basement of Olson Pavilion.

Specimens will be stored for up to 70 years, after which they will be destroyed.

10.2 Data to be stored or associated with each specimen.

Specimens will be coded; meaning that a key will exist that can link the codes back to the direct subject identifiers. Each participant will be assigned a unique study ID number that can be traced back to the study participant. The blood

PROTOCOL TITLE: Unacylated Ghrelin to Improve Functioning in PAD: the GIFT Trial

samples that are maintained in long-term storage will be labeled with this unique identifier and the date and time of the blood collection.

10.3 Procedures to release data or specimens.

Only [name] has control over release of study data or specimens. Any investigators seeking to analyze blood specimens must contact [name] for permission. Each request, if it occurs, will be considered on a case-by-case basis. [name] will obtain IRB approval prior to releasing any blood specimens for analysis, other than those tests specifically named in this application.

11.0 Data and Specimen Management

11.1 Data management.

Data is recorded using preprogrammed instruments and an electronic case report form using secure, HIPAA-compliant REDCap database software on servers maintained by Northwestern's Clinical and Translational Sciences Institute. We have substantial experience with REDCap.

Data Safety Monitoring Board (DSMB). We have identified three nationally recognized experts to serve on the DSMB.

Power Estimates. The primary aim of the GIFT Trial is to obtain preliminary data that will allow us to determine whether there is sufficient 'signal' from unacylated ghrelin to warrant additional study of unacylated ghrelin in older patients with PAD. In addition, the GIFT Trial will allow us to obtain an estimate of effect size and standard deviation of change in our study outcomes when unacylated ghrelin is administered to older PAD participants. Finally, the GIFT Trial will allow us to determine the feasibility of administering unacylated ghrelin to older patients with PAD. Because this is a preliminary study, no power calculations were performed.

Statistical Analyses. Simple statistics will be performed to assess changes in brachial artery FMD over time in response to each unacylated ghrelin injection. Simple statistics will also be performed to analyze changes in levels of unacylated ghrelin and acylated ghrelin and circulating levels of oxidative stress after each subcutaneous injection of unacylated ghrelin.

11.2 Power analysis.

A power analysis is not applicable, given the exploratory nature of this research.

11.3 Steps to secure data to maintain confidentiality during storage, use, and transmission.

First, all research assistants must complete training in protection of subject privacy and prevention of disclosure of identifying information.

PROTOCOL TITLE: Unacylated Ghrelin to Improve Functioning in PAD: the GIFT Trial

Second, all data collection forms are maintained in a secure office space.

Third, our study databases are maintained in locked computer files or on secure hard-drives that are password protected; to which only authorized staff have access. [name] or a study manager must provide permission for programmers and research assistants to access study databases.

Fourth, a study identification number will be assigned to each participant. This identification number will be used to label blood specimens, for example. In addition, most pages of our data collection forms will have only the study identification number listed (and not the participant's name, for example).

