Specific Aim. Because subcutaneously administered unacylated ghrelin has not been studied in humans, we will establish the association of increasing doses of subcutaneous unacylated ghrelin with circulating levels of unacylated ghrelin and brachial artery flow-mediated dilation (FMD) and levels of circulating inflammatory biomarkers. To achieve this aim, six PAD participants age 55 and older will receive a single subcutaneous injection of unacylated ghrelin at doses of 10 ug/kg, 20 ug/kg, and 40 ug/kg, respectively, on three separate days at least one week apart. Unacylated ghrelin levels will be measured at baseline and at defined intervals after each subcutaneous injection (30 minutes, 60 minutes, 1.5 hours, 3 hours, 6 hours, 8 to 12 hours and 24 hours). Brachial artery FMD will be measured at baseline, before the unacylated ghrelin injection, approximately six to eight hours, and 24 hours after each unacylated ghrelin injection (8). Circulating levels of inflammatory biomarkers will be measured at baseline and at six hours, 8-12 hours, and 24 hours after the subcutaneous injection of unacylated ghrelin. The lowest dose of subcutaneously delivered unacylated ghrelin that maximizes brachial artery FMD, maximizes levels of unacylated ghrelin, and minimizes circulating levels of inflammatory biomarkers will be used in future study.

PROTOCOL TITLE: Unacylated Ghrelin to Improve Functioning in PAD: the GIFT Trial

Specific Aim 2. We will assess the safety of increasing doses of unacylated ghrelin in six patients with PAD age 55 and older.

1.2 *Hypotheses.*

We hypothesize that unacylated ghrelin, administered subcutaneously, will increase brachial artery flow-mediated dilation (FMD) and reduce circulating levels of inflammatory biomarkers and that higher doses of subcutaneously administered unacylated ghrelin will be associated with greater increases in brachial artery FMD and lower circulating levels of inflammatory biomarkers.

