7.0 Study Timelines

Each participant's part in this study will last up to approximately six months.

Visit 1.

The initial visit will last approximately 2 hours. Informed consent will be provided and an ankle brachial index (ABI) measurement will be obtained to ascertain eligibility. Questionnaires will be administered to obtain information about their health and medical history. The six-minute walk test and the four-meter walking velocity at usual and fastest pace may be obtained. An electrocardiogram (ECG) will be performed and a blood sample will be obtained. Blood will be tested for liver and kidney function, electrolytes, and a complete blood count (CBC). A physical exam will be performed and medical history will be obtained. Height and weight will be measured. Vitals may be obtained. Vitals include blood pressure, heart rate, respiratory rate, temperature, and oxygen level.

Visits 2, 5, and 8.

Visits 2, 5, and 8 will last approximately 8-12 hours and will be separated by at least one week. We plan to collect data for each dose on all six participants before proceeding to the next dose. At visits #2, #5, and #8, respectively, participants will receive a subcutaneous injection of unacylated ghrelin of the following doses:

Visit 2: 10ug/kg

Visit 5: 20 ug/kg

Visit 8: 40 ug/kg

Prior to the injection. Prior to the injection, blood will be drawn and measured for levels of unacylated ghrelin and acylated ghrelin, inflammatory biomarkers, liver and kidney function, electrolytes, and CBC. Blood pressure and pulse will be obtained seated and in the standing position. Brachial artery flow-mediated dilation (FMD) will be measured.

30 minutes, 60 minutes, 90 minutes, and 3 hours and 6 hours post-injection.

A blood sample will be obtained and measured for levels of unacylated ghrelin and acylated ghrelin. Blood pressure and pulse will be obtained seated and in the standing position. A brachial artery FMD may be measured at 6 hours (e.g. if we do not see a change in brachial artery FMD 8-12 hours post-injection, we may want to move the collection time point to 6 hours).

8-12 hours post-injection. A blood sample will be obtained and measured for levels of unacylated ghrelin and acylated ghrelin as well as inflammatory markers.

PROTOCOL TITLE: Unacylated Ghrelin to Improve Functioning in PAD: the GIFT Trial

Blood pressure and pulse will be obtained seated and in the standing position. Brachial artery FMD may be measured.

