Additional vitals will be obtained at the discretion of the CRU nurse throughout the visit. Vitals include blood pressure, heart rate, respiratory rate, temperature, and oxygen level. Participants will be administered a questionnaire to assess symptoms. Participants may be asked to take their medications in the evening rather than the morning on the day of injection visits.

Participants may also be asked to repeat the six-minute walk and/or four-meter walks performed at baseline.

Visits 4 and 7.

At visits 4 and 7, a blood sample will be obtained and tested for liver and kidney function, electrolytes, and CBC. The physical exam and medical history may be repeated. Weight may be re-measured.

Visits 3, 6, and 9.

Visits 3, 6, and 9 will occur approximately 24 hours after the subcutaneous injections given at visits 2, 5, and 8, respectively. A blood sample will be obtained and measured for levels of unacylated ghrelin and acylated ghrelin as well as inflammatory markers and liver and kidney function, electrolytes, and CBC. Blood pressure and pulse will be obtained seated and in the standing position. Brachial artery FMD will be measured and an ECG will be performed. Vitals may be obtained at the discretion of the CRU nurse. Participants will be administered a questionnaire to assess symptoms.

Prior to FMD measures, the participant will be asked to consume a low calorie, low fat meal provided to the participant by CRU nutrition services.

The table below lists timing of the outcome and safety measures.

Measures	Prior to Injection *	30 minutes	60 minutes	90 minutes	3 hours	6 hours	8-12 hours	24 hours
Safety Measures								
Electrocardiogram	X*							X
Comprehensive chemistry panel	X*							X
CBC	X*							X
Pulse and blood pressure	X	X	X	X	X	X	X	X
Orthostatic pulse and blood pressure	X	X	X	X	X	X	X	X

PROTOCOL TITLE: Unacylated Ghrelin to Improve Functioning in PAD: the GIFT Trial

Efficacy outcome measures								
Unacylated and acylated ghrelin levels	X	X	X	X	X	X	X	X
Inflammatory biomarkers	X						X	X
Brachial artery FMD	X					X	X	X

*The ECG, comprehensive chemistry panel (liver and kidney function and electrolytes), and CBC will be obtained at visit #1 for the 10 ug/kg dose.

**The FMD will be performed at either 6 hours or 8-12 hours.

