We will test doses of 10 ug/kg, 20 ug/kg, and 40 ug/kg of unacylated ghrelin on three separate days for each participant. These doses were selected based on published literature and the experience of our consultants [name], who has an ongoing study of intravenously administered unacylated ghrelin in healthy people (R01-DK097550) and [name], who has an ongoing study of subcutaneously administered acylated ghrelin in older frail people without PAD (R21-AG040488).

Justification for proposed doses of unacylated ghrelin. Unacylated ghrelin is a synthetic 28 amino-acid protein. The ½ life of intravenously administered unacylated ghrelin is 30-34 minutes, which is comparable to but slightly longer than the ½ life of insulin and glucagon (9). In comparison, the ½ life of intravenously administered acylated ghrelin is 9 to 11 minutes (9). A portion of intravenously administered acylated ghrelin is converted to unacylated ghrelin (9). In contrast, unacylated ghrelin is not converted to acylated ghrelin (9). In healthy people, circulating levels of unacylated ghrelin are higher than those of acylated ghrelin, in a ratio that is typically 4:1 but ranges from 2:1 to 9:1 (9,11,48). In a study of healthy people, a 4X higher dose of intravenously administered unacylated ghrelin achieved a CMax that was twelve times higher than that for intravenously administered acylated ghrelin (9). Because of the longer ½ life of unacylated ghrelin and the substantially greater CMax achieved with unacylated ghrelin as compared to acylated ghrelin, we will begin with a subcutaneous unacylated ghrelin (10 ug/kg) dose that is comparable to that selected by [name] for her study of subcutaneously administered acylated ghrelin. Next, we will test a subcutaneous dose of unacylated ghrelin that is 2X the starting dose (20 ug/kg). Finally, we will test a subcutaneous dose of unacylated ghrelin that is 4X times the starting dose (40 ug/kg). Four times the starting dose was selected as the maximal dose to test because circulating levels of unacylated ghrelin are approximately four times higher than circulating levels of acylated ghrelin and because of the higher CMax of unacylated as compared to acylated ghrelin (9,11,48). Although the GIFT Trial will administer unacylated ghrelin subcutaneously, we anticipate that, similar to intravenous administration, the maximum concentration of unacylated ghrelin will be greater than that for acylated ghrelin.

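### The analysis text names no between-dose comparison of FMD change, and the same-day FMD time may be moved once results are seen, so a time difference can enter the dose choice

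*Combined protocol and SAP*

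**What the plan says.** **What the dose choice needs.** Section 1.2 hypothesizes that "higher doses of subcutaneously administered unacylated ghrelin will be associated with greater increases in brachial artery FMD". Section 9.1 picks the lowest dose that gives the largest FMD. Its worked example turns on whether the FMD improvement at 20 and at 40 ug/kg is alike. Each of six participants is to receive all three doses.

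**What is to be analyzed.** Section 11.1 is the only analysis text: "Simple statistics will be performed to assess changes in brachial artery FMD over time in response to each unacylated ghrelin injection". The other markers are treated the same way, injection by injection. The section also promises an effect size and an SD of change. It names no comparison between doses and no interval.

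**When FMD is read.** Every dose has a reading before injection. For the readings after it:
- Section 1.1 (Specific Aim): "approximately six to eight hours, and 24 hours after each unacylated ghrelin injection".
- Section 7.0, footnote to the schedule table: "The FMD will be performed at either 6 hours or 8-12 hours". Sections 8.1 and 14.0 give the same two options.
- Section 7.0, injection visits: "if we do not see a change in brachial artery FMD 8-12 hours post-injection, we may want to move the collection time point", the new time being 6 hours.
- Section 7.0, Visits 3, 6 and 9 (about 24 hours after each dose): "Brachial artery FMD will be measured and an ECG will be performed".

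**Order of work.** Section 7.0: "We plan to collect data for each dose on all six participants before proceeding to the next dose". Section 9.1 repeats this.

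**Replacement.** Under Section 13.0, a replacement enters at the dose the withdrawn participant would have received next.

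**The concern.** There are two linked gaps.

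First, the quantity that the decision uses is the difference in FMD change between two doses in the same person. The planned summaries are changes within each dose. Three separate within-dose summaries do not show how precisely the doses can be told apart. With six people, two doses may look alike because they are alike or because the data cannot separate them, and without an interval the reader cannot tell which.

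Second, no section requires the same-day FMD to be read at the same time at all three doses, and one section lets an observed FMD result prompt a change of time. The stated reason for moving, no change at the later time, itself implies that the response may differ between the two times. If the lower dose is read at one time and the higher dose at another, a time effect can be taken for a dose effect, possibly in the direction the trial hypothesizes.

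Dose selection is a stated purpose of this pilot (Sections 1.1, 9.1 and 9.3). It stands beside the aim in Section 11.1 of finding out whether there is enough signal to justify further study.

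**Working it through.** The documents contain no power calculation, effect size or SD of FMD change, so there is no figure of theirs to reproduce. The reproducibility figure in Section 9.2 describes the reading laboratory, not the variation of a participant's FMD change between dosing days, and cannot stand in for that SD.

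**1. What a move does to the contrast.** Let the mean change be D10 + T(late) at 10 ug/kg, read at 8-12 hours, and D20 + T(6 h) at 20 ug/kg, read at 6 hours. Then

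20 minus 10 = (D20 - D10) + d, with d = T(6 h) - T(late).

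If all six are read at the new time at 20 ug/kg and none at 10 ug/kg, d enters in full. If the move came part-way through the 10 ug/kg dose, with m of six already read at 6 hours, the contrast contains d x (1 - m/6). For m = 3 that is d/2. Nothing in the data separates d from the dose difference, except the 24-hour reading, which is taken at the same nominal time at every dose.

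**2. Precision of a paired dose difference.** With k complete pairs, the 95% CI half-width in units of the SD of the paired difference is t(0.975, k-1)/sqrt(k):

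| Pairs | t | Half-width |
|---|---|---|
| 6 | 2.571 | 2.571/2.449 = 1.05 |
| 5 | 2.776 | 2.776/2.236 = 1.24 |
| 4 | 3.182 | 3.182/2.000 = 1.59 |

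The documents give no SD. If it were 2 to 4 FMD points (an assumption), six pairs would give 2.1 to 4.2 points.

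**3. Illustration of what a time effect can do to the choice.** Assumptions: FMD alone decides; all three doses are truly equal; the SD of one participant's change is 1; n = 6; changes at different doses correlate at r = 0 to 0.5; the lowest dose whose mean lies within 0.5 SD of the best mean is chosen; any move is made after the first dose regardless of the data.

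With the first-dose mean as reference,

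P(lowest dose chosen) = integral of phi(z) x Phi(z + c)^2 dz, c = (0.5 - d) x sqrt(6)/sqrt(1 - r).

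- Common time, d = 0: c = 1.225 at r = 0 gives 70%; c = 1.732 at r = 0.5 gives 82%.
- Time moved, d = 0.5 SD: c = 0 at any r gives 33%, because the time effect uses up the whole margin.

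**4. Complete pairs or all available data after one replacement.** For two doses with five complete pairs and one unpaired reading at each dose, in SDs of change:

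- complete pairs: SE = sqrt(2(1 - r)/5)
- all available, difference of the two means: SE = sqrt(1/3 - 10r/36)

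At r = 0.5 these are 0.447 and 0.441; at r = 0.75 they are 0.316 and 0.354. They are equal where 0.4 - 0.4r = 0.333 - 0.278r, so r is about 0.55. Neither is always better, and r is unknown. The paired estimate matches the question, so it can be the main one, with all available data as the sensitivity analysis.

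**The case against.** **It is a six-person exploratory pilot with no inference planned.** This stands as far as power and testing go, and neither is asked for. Change after each injection also serves the signal aim of Section 11.1 directly. But the same document uses the data to choose among doses, and that use needs the between-dose difference and its uncertainty.

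**Simple statistics can include paired differences, and Section 9.1 already compares doses.** Both are true. A reader might infer that the plan rules out a paired comparison; it does not. What is missing is the named contrast, its interval and a common measurement time.

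**The documents do not say that a move would fall between doses.** Correct. A reader might infer that it must, since each dose is to be finished in all six first. Section 7.0 says only that the time may be moved, not when. A move within a dose is also possible; it would mix times inside one dose mean.

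**The 24-hour FMD already gives a common time.** It does, and the fix relies on it. However, the endpoint section (8.1) names only the same-day reading after injection.

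**Intervals this wide will rarely settle the choice.** Probably so. Showing that is useful, because it tells the designers of the next trial how firmly the dose was chosen.

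**Conclusion.** The point holds as a gap that is cheap to close. Followed as written, the plan can compare doses on FMD read at different times after injection, and it does not commit to estimating the difference on which the choice rests.

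Its size depends on quantities the documents do not give. The half-widths of 1.05, 1.24 and 1.59 SDs of the paired difference need only the number of pairs and approximate normality. The fall from 70%-82% to 33% rests on an assumed time effect, margin and correlation.

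Three stronger readings are not supported:
- That these percentages are the protocol's error rates. Its rule also weighs oxidative stress and ghrelin level, and the illustration treats the move as made without regard to the data.
- That moving the time after a poor first-dose result biases the contrast even with no time effect. A low first-dose mean will tend to be followed by a higher one whether or not the time is moved. That is regression to the mean, not a result of moving.
- That the intravenous half-life in Section 7.0 shows which FMD time is best. The documents give no subcutaneous half-life, and FMD is a vascular response, not a plasma level.

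A common time does not remove the confounding of dose with period that comes with the fixed ascending order. That is a separate limit of the design.

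**What to change.** **(a) Timing.** Before the first dose, fix one same-day FMD time with a narrow window for all three doses, and bring Sections 1.1, 7.0 (visit text and table footnote), 8.1 and 14.0 into line with it. Naming 8-12 hours alone would not be enough: that window is four hours wide, more than the two hours between 6 and 8. If the time is moved anyway, base the between-dose comparison on the 24-hour FMD and show the same-day readings separately by time.

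**(b) Analysis, Section 11.1.** Define the dose comparison as the within-participant difference in FMD change from the same-day pre-injection value, for 20-10, 40-20 and 40-10, each with a 95% CI. Estimate it from participants who received both doses, and state the number of pairs. If anyone is replaced under Section 13.0, add the all-available-data result as a sensitivity analysis. Report the biomarkers in the same way.

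**Cost.** Analysis wording and one procedural decision; no added visits, scans or samples. The option to move the FMD time is given up, or loses its role in choosing the dose. The 24-hour fallback may miss a short effect. The intervals will be wide.

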9.0 Procedures Involved

9.1 Study design.

STUDY OVERVIEW. We will identify the lowest subcutaneous dose of unacylated ghrelin that maximizes brachial artery flow mediated dilation (FMD). These PAD participants will receive three different subcutaneous doses of unacylated ghrelin on three different days and will undergo measurement of unacylated ghrelin levels prior to the injection and at specified time intervals. Each dose will be separated by a wash-out period of \geq one week. Data will be obtained for all six participants at each dose before moving to the next dose. We will test doses of 10 ug/kg, 20 ug/kg, and 40 ug/kg of unacylated ghrelin on three separate days for each participant. These doses were selected based on published literature and the experience of our consultants [name], who has an ongoing study of intravenously administered unacylated ghrelin in healthy

PROTOCOL TITLE: Unacylated Ghrelin to Improve Functioning in PAD: the GIFT Trial

people (R01-DK097550) and [name], who has an ongoing study of subcutaneously administered acylated ghrelin in older frail people without PAD (R21-AG040488).

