Risks associated with blood draws. The potential risks of drawing blood include a bruise at the site of vein puncture, inflammation of the vein, and infection. Participants may experience lightheadedness or dizziness or fainting after injections. Care will be taken to avoid these complications.

Risks associated with holding medications for study testing. Participants may be asked to take their medications in the evening rather than in the morning on the day of study drug injections. This change in medication dosing may result in higher levels of blood pressure during the day with potentially adverse consequences, including increased risk of stroke or need for evaluation in the Emergency Department. However, participants will be carefully monitored for their blood pressure level throughout the day.

Risks associated with questionnaire administration. Participation includes a risk of loss of confidentiality regarding personal health information. However, all research staff has undergone formal human subjects training. They are trained to protect the privacy of research subject participants.

In addition, administration of unacylated ghrelin may have risks to the subjects that are currently unforeseeable.

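### With no drug-free FMD day, the same-day FMD change cannot separate drug effect from time of day, and section 11.1 should limit what is read from it

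*Combined protocol and SAP*

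**What the plan says.** The analysis text in section 11.1 is one sentence for FMD: "Simple statistics will be performed to assess changes in brachial artery FMD over time in response to each unacylated ghrelin injection". It names no comparator, model, test or decision rule. The same section says the pilot should show whether there is enough signal to justify further study, and should supply an effect size and the SD of change.

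The design is in sections 7.0 and 9.1. "These PAD participants will receive three different subcutaneous doses of unacylated ghrelin on three different days", and "Data will be obtained for all six participants at each dose before moving to the next dose". The order is therefore fixed and ascending, ending with "Visit 8: 40 ug/kg". No vehicle, sham or no-injection day with FMD is described. Visits 4 and 7 have no injection, but no FMD is listed for them, and none is listed for visit 1.

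The FMD times differ between sections:
- **1.1 (Specific Aim):** before injection, about 6 to 8 hours, and 24 hours.
- **7.0, text:** before injection and at 24 hours; FMD is optional at 6 hours and at 8-12 hours, and the reading may be moved to 6 hours if no change appears at 8-12 hours.
- **7.0, table:** both 6 and 8-12 hours are marked, with a note that only one will be done.
- **8.1 and 14.0:** baseline and 6 or 8-12 hours; 24 hours is not mentioned.

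On the 24-hour reading, section 7.0 says "Visits 3, 6, and 9 will occur approximately 24 hours after the subcutaneous injections given at visits 2, 5, and 8". Section 1.2 also hypothesizes that "higher doses of subcutaneously administered unacylated ghrelin will be associated with greater increases in brachial artery FMD".

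**The concern.** The pre-injection and post-injection readings on an injection day fall at different clock times. Around them lie hours of observation, repeated blood draws, an optional walk at about 4 to 8 hours (9.2) and possibly a shift of medications to the evening (7.0). For that shift, section 14.0 says "This change in medication dosing may result in higher levels of blood pressure during the day". So the protocol itself recognizes a possible vascular influence on injection days that is not the study drug.

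Anything that moves FMD between the two readings is counted in section 11.1 as response to the injection. It enters the go-ahead decision and the effect size carried into the next trial. The option to move the reading when no change is seen adds selection in favour of change. If it is used between doses, the doses are also no longer compared at the same time after injection.

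**Working it through.** **No figure to reproduce.** The plan gives no power calculation, alpha, SD of FMD change or size of any time-of-day effect. What follows is an illustration on assumed values.

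**What can be identified.** Let D_k be the change from pre-injection to post-injection FMD at dose k, with drug effect δ_k and same-day shift s_k:

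E(D_k) = δ_k + s_k

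With no drug-free FMD day, s_k cannot be estimated, so the bias in the per-dose effect is s_k in full. If the shift is the same on all three days, E(D_40 − D_10) = δ_40 − δ_10 and it cancels. The change from pre-injection to 24 hours is taken at about the same clock time, so it is largely free of a time-of-day shift.

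**Inputs.** From the plan: n = 6, three doses, each person receiving all three. Assumed: true drug effect zero; common shift d in units of the SD of same-day change; normal changes; correlation 0.3 between one person's changes on different days; one-sample t test on 5 df, called positive above t = 2.571 (upper 2.5% tail).

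**One dose.** T is noncentral t with 5 df and noncentrality d√6. At d = 0.5 this is 0.5 × 2.449 = 1.225, and P(T > 2.571) = 17%.

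**At least one of three doses, and the contrast** (simulation, 200,000 trials):

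| Shift d (SD) | One dose positive | At least one of three | 40 minus 10 ug/kg positive |
|---|---|---|---|
| −0.5 | 0.1% | 0.4% | 2.5% |
| 0 | 2.5% | 7% | 2.5% |
| 0.25 | 7% | 19% | 2.5% |
| 0.5 | 17% | 39% | 2.5% |
| 1.0 | 51% | 83% | 2.5% |

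With correlation from 0.5 down to 0, the any-dose figure is 36-43% at d = 0.5 and 78-88% at d = 1.0. If signal meant only a mean change above zero, one dose would pass with probability Φ(d√6): 50% at d = 0, 89% at 0.5 and 99% at 1.0.

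**Precision of the contrast.** The SD of D_40 − D_10 is √(2 × (1 − 0.3)) = 1.183. The 95% confidence interval half-width is 2.571 × 1.183 / √6 = 1.24 SD, against 2.571 / √6 = 1.05 SD for a single dose. For true effects of 0.25, 0.5 and 1.0 SD at the three doses, the 40 minus 10 difference is 0.75, the noncentrality is 0.75 / 1.183 × 2.449 = 1.55, and power is 24% (25% for the slope on dose). For 0.5, 0.75 and 1.0 SD the difference is 0.5, and power is 13%.

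**Visit order.** With no drug effect but a same-day change that drifts by 0, 0.25 and 0.5 SD over the three injection days, the contrast is positive 13% of the time; with 0, 0.5 and 1.0 SD, 39%. The 13% equals the power for a real difference of 0.5 SD, because in a fixed ascending order the two cannot be told apart. Pre-injection FMD could stay constant while the same-day change drifts, so checking it would not reveal this.

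**The case against.** The strongest reply is that this is an exploratory pilot with no stated test, so the 2.5% rule is not the plan's, and that much of the remedy is already there. FMD is collected at 24 hours. Section 9.1 chooses a dose by comparing FMD improvement between doses, and a common shift cancels from that comparison when the time after injection is fixed. A low calorie, low fat meal is provided before FMD measures, which limits one source of variation.

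Much of this stands. The percentages are illustrative, and the shared shift acts on whether there is a signal and how large it is, rather than on the choice between doses. What does not follow is that nothing needs to change. An exploratory label explains the missing power calculation, but it does not remove a bias that feeds the next trial's effect size. Section 8.1 leaves the 24-hour reading out of the endpoint, and section 11.1 does not rest the signal on it or on any between-dose comparison.

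A reader might also infer more than the documents support:
- **That the protocol expects blood pressure, and with it FMD, to change between the readings.** Section 14.0 gives higher daytime pressure only as a possible risk, and the medication shift is optional. No pre-to-post change is stated, and the walk could come after a 6-hour FMD.
- **That the bias must be upward.** No direction is given. At −0.5 SD the any-dose figure falls to 0.4%, so a real effect could be masked.
- **That the dose trend should replace the per-dose change as the signal.** It cancels only a shift that is the same on all days, it is fully confounded with visit order, and its power here is about 13-25%.

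**Conclusion.** The concern holds in a limited form. The same-day FMD change at 6 or 8-12 hours cannot distinguish drug effect from time of day or other same-day influences, and section 11.1 would credit a shared shift to the injection. The bias in the estimated effect equals the shift, in either direction.

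Its actual size is unknown. The 7%, 19%, 39% and 83% figures depend on an assumed common shift, correlation, normality and tail rule, and should not be read as this trial's false-positive rate. Nor do the documents show that any apparent signal would be false; they show that this comparison alone could not establish it as real. The point deserves correction because it bears on the pilot's main output and changes to the analysis text largely address it.

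**What to change.** Amend section 11.1 as follows:

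1. Analyse same-day FMD change at one post-injection time, fixed in advance and identical at all three doses. Reconcile the FMD times in 1.1, 7.0 (text and table), 8.1 and 14.0, and remove the option to move the reading because no change was seen.
2. Alongside the per-dose changes, report within-person contrasts (40 minus 10 ug/kg, and the slope over the three doses) and the 24-hour minus pre-injection change, all with confidence intervals.
3. State that a similar change at all three doses cannot be separated from time of day, and will not by itself be taken as drug signal or used as the effect size for the next trial.

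The cost is text only, with no new visits, participants or procedures. The limits should be stated with it:
- The contrasts are imprecise with six people.
- Dose is confounded with visit order, and pre-injection FMD would not detect a drift in same-day change.
- A plateau already reached at the lowest dose gives a flat trend, which would leave effect and time of day unseparated.
- The 24-hour reading may miss a short-lived effect. The stated intravenous half-life is 30-34 minutes, so 24 hours is about 1,440/34 = 42 to 1,440/30 = 48 half-lives, although subcutaneous kinetics are not known.
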